5.1.2 Visit Windows

For data collected at multiple time points, the scheduled collection date/time will be used to summarize the data, unless otherwise indicated. Visits are scheduled from time of previous cycle's Day 1.

Scan assessments are scheduled from the reference date (date of first dose). Scan dates are not associated with a visit number. Dates are used for analyses and patient listings.

Unscheduled assessments will not be taken into account in summary variable calculations, except for baseline assessments and unscheduled RECIST, bone scan, PSA and HRQoL evaluations for evaluating efficacy (Section 8). All measurements will be presented in the listings.

Unless otherwise indicated, if more than one measurement (a lab result for example) exists for a patient on a particular time point/visit, the last value obtained at that time point/visit will be used when summarizing the data.

Refer to protocol section 6.1 and protocol Appendix 1 for schedules of study assessments during each study period.

5.2 Partial/Missing Dates

In general, the database requires a valid full date, including dates used for the alternate primary endpoints, rPFS and OS. However, for partial or missing dates for initial cancer diagnosis, prior therapies, and concomitant medication start dates, the rules shown below will be applied. (Concomitant medication stop dates and start and end dates for adverse events, concurrent radiotherapy, and concurrent surgical/therapeutic procedures are full date required fields.)

The imputed dates will only be used for the assignment to prior and/or concomitant medication or concurrent therapy and for deriving time since initial cancer diagnosis. The imputed dates will not be used in any other calculation and will not be listed.

For the calculation of the time since initial cancer diagnosis, the following imputation rules will be applied when the date of initial cancer diagnosis is incomplete:

- If the day is missing: first day of the month.
- If the day and month are missing: first day of January.

For the assignment of medication, therapy and procedure to prior or concomitant/concurrent collected on the Concomitant Medication/Therapy, Concurrent Surgical / Therapeutic Procedures, and Radiotherapy CRF pages, the following rules will be applied for incomplete dates:

- If start date is incomplete:
 - if end date is before the date of first dose of randomized treatment, the start date will remain missing (i.e. prior);
 - if end date is on or after date of first study drug administration or the medication is ongoing,
 - if the day is missing: the start date will be imputed with the first day of the month;
 - if the day and month are missing: the start date will be imputed with 01 January of the year.

Note: Prior cancer related therapies, procedures and medications with missing or partial dates as captured on the Prior Cancer Related Surgery, Prior Radiotherapy and Prior Cancer Systemic Therapy CRF pages will not be imputed or included in the assignment of medications, procedures or therapies to prior or concomitant. Prior cancer related therapies will be summarized separately as described in Section 7.4.

The following rule should be used for the imputation of the date of last administration (end date) for BSC/BSoC:

- If the end date is completely missing and there is no End of Treatment (EOT) page and no death date/End of Study (EOS) date, the patient is considered as on-going. The patient should be treated as on-going and the cut-off date should be used as the end date.

After imputation, compare the imputed date with start date of BSC/BSoC, if the imputed date is < start date of BSC/BSoC: Use the BSC/BSoC start date.

The following rules will be used for imputing adverse event (AE) start dates to assign as treatment emergent:

If day, month and year are missing:

- Completely missing start dates will not be imputed.

If day and month are missing:

- If partial start date year = year of randomized treatment start date then
 - If end date contains a full date and end date is earlier than randomized treatment start date then set start date = 01 January of the year
 - Else set start date = randomized treatment start date.
- If partial start date year > year of randomized treatment start date then 01 January of the year
- If partial start date year < year of randomized treatment start date then 01 July of the year

If day is missing:

- If partial start date month and year = month and year of randomized treatment start date then
 - If end date contains a full date and end date is earlier than randomized treatment start date then set start date= first day of the month and year.
 - Else set start date = randomized treatment start date.
- If partial start date month and year > month and year of randomized treatment start date then first day of the month and year
- If partial start date month and year < month year of randomized treatment start date then 15th day of the month and year

Note: If randomized treatment start date is missing, apply the same rules but use the ⁶⁸Ga-PSMA-11 administration date instead.

For the assignment of an adverse event as a randomized treatment-emergent adverse event, the following rules will be applied when there is a partial date of subsequent anti-cancer treatment as captured on the post-treatment anti-cancer therapies or procedures CRF pages:

- if the day is missing: if the month of the partial subsequent anti-cancer treatment is in the same month as the date of last administration of randomized treatment (see Section 5), then impute using the date of last administration of randomized treatment. Otherwise, impute using the first day of the month.

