If the patient meets all of the criteria above, and agrees to continue with additional treatment of ¹⁷⁷Lu-PSMA-617, the investigator may administer a further 2 cycles. A maximum of 6 cycles of radioligand therapy is allowed. If the patient does not meet any of the criteria or does not agree to additional ¹⁷⁷Lu-PSMA-617 treatment, then no additional doses of ¹⁷⁷Lu-PSMA-617 will be administered after Cycle 4. After the last cycle of ¹⁷⁷Lu-PSMA-617, patients can continue BSC/BSoC alone.

BSC/BSoC for each patient will be selected at the discretion of the patient's physician, prior to randomization and will be administered per the physician's orders and continued until the patient comes off the treatment part of the study and enters the long-term follow-up stage.

A patient may choose to discontinue the randomized treatment part of the study at any time. If a patient chooses only to discontinue from the randomized treatment in the study for a reason other than radiographic progression, the patient will be asked to confirm if they consent to continue to be followed for long term safety, radiographic Progression-Free Survival (rPFS), and survival follow up. The patient will continue to be followed for long term follow up unless they specifically withdraw consent from long term follow-up of the study. Crossover to ¹⁷⁷Lu-PSMA-617 treatment is not allowed.

An End of Treatment (EOT) visit should occur once a patient discontinues randomized treatment for any reason (patient or investigator decision, going on to long term follow up, etc.). The EOT visit should occur approximately 30 days from the last dose of ¹⁷⁷Lu PSMA-617 or the date of the best supportive/best standard of care end of treatment decision (whichever is later), but before the initiation of subsequent anti-cancer treatment, outside of what is allowed on study.

After the EOT visit, patients will enter the long-term follow-up period. The long-term follow-up period will include the collection of rPFS (if discontinuing for reasons other than radiographic progression), survival and information about new treatments, along with the patient's response to these treatments, adverse events assessment, and results of hematology and chemistry testing. During follow-up, patients will be followed for safety and survival. They will be contacted every 3 months (± 1 month) via phone, email, or letter for up to 24 months or until 508 deaths have occurred, whichever is sooner.

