Vital signs at baseline	the last available assessment on or before the date of start of randomized treatment or if a time assessment is captured, the 15 minutes pre-dose value on or before the date of start of randomized treatment	Safety for randomized treatment
Vital signs at screening	the last available assessment on or before the date of ⁶⁸ Ga-PSMA-11 dosing	Safety for ⁶⁸ Ga-PSMA-11
ECG at baseline	the last available assessment on or before the date of start of randomized treatment	Safety for randomized treatment
ECG at screening	the last available assessment on or before the date of ⁶⁸ Ga-PSMA-11 dosing	Safety for ⁶⁸ Ga-PSMA-11
1. For the sub-study, randomized treatment refers only to ¹⁷⁷ Lu-PSMA-617+BSC/BSoC.		

Cycle 1 Day 1 (C1D1) is date of first study procedures, randomized treatment and assessments.

Date of randomization is used for the start date of "time to" endpoints for efficacy analyses.

⁶⁸Ga-PSMA-11 dosing is the date ⁶⁸Ga-PSMA-11 was administered.

Date of last randomized treatment administration is the date of last administration of randomized treatment which is the date of last administration of ¹⁷⁷Lu-PSMA-617 or date of last administration of BSC/BSoC, whichever is later. For example: if the last dose administration of ¹⁷⁷Lu-PSMA-617 is on 15APR2019, and the end of treatment decision

date for BSC/BSoC is on 17APR2019, then the date of last administration of randomized treatment is on 17APR2019.

- Date of last administration of ¹⁷⁷Lu-PSMA-617 is the last date when ¹⁷⁷Lu-PSMA-617 was administered (non-zero dose), i.e. the latest date of administration as captured on the ¹⁷⁷Lu-PSMA-617 Administration CRF page with a non-zero dose.
- Date of last administration of BSC/BSoC is the end of treatment decision date recorded on the End of Treatment – BSC/BSoC CRF.
- Date of last administration of a NAAD as study BSC/BSoC will be defined as follows:
 - = latest end date of a NAAD indicated as study BSC/BSoC (captured on concomitant medications CRF) if before date of last administration of BSC/BSoC, otherwise
 - = date of last administration of BSC/BSoC.

For example: if the latest end date of a NAAD indicated as study BSC/BSoC is 01AUG2019 and the date of last administration of BSC/BSoC is 03OCT2019, then the date of last administration of a NAAD as study BSC/BSoC is 01AUG2019.

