9.2.1 Definition of Treatment Emergent Adverse Events (TEAEs)

⁶⁸GA-PSMA-11

PSMA-617-01 SAP Version 3.0
18Jan2021

Page 53 of 79

This information is confidential or privileged information and trade secrets of Endocyte, Inc.

A ^{68}Ga -PSMA-11 TEAE is defined as an AE that was not present prior to dosing with ^{68}Ga -PSMA-11 but appeared following dosing, or was present at time of dosing but worsened during or after dosing.

The treatment-emergent period will be defined as the period from the date of ^{68}Ga -PSMA-11 dosing up to 6 days after the date of ^{68}Ga -PSMA-11 dosing as long as prior to the first dose of ^{177}Lu -PSMA-617 for the investigational arm and prior to Cycle 1 Day 1 for the BSC/BSoc arm.

AEs reported as "possibly", "probably", or "definitely" related to ^{68}Ga -PSMA-11 that occur beyond the 6-day reporting window but occur before the initiation of randomized treatment are also ^{68}Ga -PSMA-11 TEAEs. Unrelated ^{68}Ga -PSMA-11 AEs that occur beyond 6 days will not be TEAEs.

Randomized treatments

A randomized treatment TEAE is defined as an AE that was not present prior to initiation of randomized treatment, defined as first dose of ^{177}Lu -PSMA-617 for the investigational arm and Cycle 1 Day 1 for the BSC/BSoc arm, but appeared following treatment, or was present at treatment initiation but worsened during treatment. An AE that was present at treatment initiation but resolved and then reappeared while the patient was on treatment is a TEAE (regardless of the intensity of the AE when the treatment was initiated).

The treatment-emergent period will be defined as the period from the date of initiation of randomized treatment up to 30 days after the date of the last administration of randomized treatment or the day prior to the initiation of subsequent anticancer treatment, whichever occurs first.

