9.2.2 General Convention

Any treatment-emergent event as defined in Section 9.2.1 missing the assessment of relatedness will be considered study drug-related.

In case a patient experienced the same event more than once, the maximum toxicity grade will be presented.

In all AE tables except the ones presented by Cycles, multiple occurrences of the same adverse events occurring in one individual are counted only once.

In all AE tables presented by cycle of onset, multiple occurrences of the same adverse events occurring in one individual within one cycle are counted only once.

AE summaries for ^{68}Ga -PSMA-11 and Randomized Treatment will include AEs occurring during the treatment-emergent period whereas AE summaries for Long-term Follow up will include new and existing AEs during the long-term follow-up period captured on the Long-Term Follow up CRF page. All AEs will be listed along with the information collected on those AEs. AEs will be summarized by number and percentage of patients having at least one AE, having at least one AE in each primary SOC and for each PT using MedDRA coding. The total number of events will also be provided. A patient with multiple occurrences of an AE will be counted only once in the respective AE category. A patient with multiple CTCAE toxicity grades for the same preferred term will be summarized under the maximum CTCAE toxicity grade recorded for the event. AE with missing CTCAE toxicity grade will be included in the total across all grades of the summary table.

In all AE summaries, the primary SOC will be presented alphabetically and the PTs will be sorted within primary SOC in descending frequency. The sort order for the PT will be based on their frequency in the ^{177}Lu -PSMA-617+BSC/BSoc arm for randomized treatment and long-term follow-up AE summaries and the frequency in the overall column for ^{68}Ga -PSMA-11 AE summaries.

9.2.3 ⁶⁸Ga-PSMA-11 Adverse Events

A summary table using the PSMA-11 Safety Analysis Set including the number of patients with at least one event, and the total number of events will be presented for the following variables:

- TEAE¹
- serious TEAE¹
- grade 3/4/5 TEAE²
- drug-related TEAE¹
- serious drug-related TEAE¹
- drug-related grade 3/4/5 TEAE²
- fatal TEAE²

¹AE variables to be tabulated by SOC and PT by grade including a total across all grades and all grades 3/4/5.

²AE variables to be tabulated by SOC and PT.

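### A missing start day for new anti-cancer therapy is imputed so early that the randomized-treatment TEAE window can close the day before last administration

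*SAP*

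**What the plan says.** Four parts of the plan act together.

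- **Imputation (SAP 5.2).** The rule is for classifying AEs: "For the assignment of an adverse event as a randomized treatment-emergent adverse event, the following rules will be applied" when the start of subsequent anti-cancer treatment is only partly known. If the day is missing and the month is that of last administration, the date of last administration is used; in any other month, the 1st. In the SAP's words: "then impute using the date of last administration of randomized treatment. Otherwise, impute using the first day of the month".
- **Window (SAP 9.2.1; same limits in Protocol 8.8.2).** The treatment-emergent period has two possible ends. One is day 30 after last administration. The other depends on new therapy and is worded thus: "or the day prior to the initiation of subsequent anticancer treatment, whichever occurs first".
- **Anchor (SAP Section 5, General Analysis Definitions).** Last administration is the later of the last 177Lu-PSMA-617 dose and the end-of-treatment decision date for BSC/BSoC. In the SAP's example the last dose is on 15 April 2019, and because the decision "date for BSC/BSoC is on 17APR2019, then the date of last administration of randomized treatment is on 17APR2019".
- **Sequence and collection.** SAP 3.1 puts the EOT visit about 30 days after that anchor, "but before the initiation of subsequent anti-cancer treatment, outside of what is allowed on study". Protocol 7.2 records AEs for the full 30 days and does not stop at new therapy.

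SAP 9.2.2 limits the randomized-treatment AE summaries to events in the treatment-emergent period.

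**The concern.** Both branches pick the earliest date compatible with a therapy that follows study treatment. The imputation can therefore only shorten the window. In the same-month branch it goes one step further: new therapy is placed on the day of last administration, and the window ends the day before new therapy, so that day itself falls outside. This looks like an unintended off-by-one between SAP 5.2 and 9.2.1.

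The consequence can be concrete. Last administration is often the BSC/BSoC end-of-treatment decision date. An AE that starts on that day and prompts the decision would not be a TEAE. It would be missing from the SAP 9.2.4 table of TEAEs leading to permanent discontinuation, and from the serious, grade 3 to 5, drug-related and fatal TEAE tables where it qualifies. The event has been collected; the imputation alone removes it.

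Two gaps sit beside this. Earlier text in SAP 5.2 confines imputed dates to prior/concomitant assignment and time since diagnosis, which, read literally, forbids the TEAE use that the same section then sets out. No rule covers a therapy date with the month missing as well.

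**Working it through.** The plan gives no figure to reproduce, so the check applies its rules to dates.

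**Definitions.** L = date of last administration; S = true start of new therapy; I = imputed start when the day is missing.

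- True window end = min(L + 30, S − 1).
- Window end under the SAP = min(L + 30, I − 1).
- I = L if S is in the same month as L; otherwise I = 1st of the month of S.

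**Same month.** I − 1 = L − 1, always. For S after L the loss is (S − 1) − (L − 1) = S − L, which is 1 to 30 days. If new therapy really began on L, nothing is lost.

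**Other month.** I is at least L + 1, so the window never closes before L. The loss is 0 to 30 days. It requires the 1st of the month to fall no later than L + 30, and S can be at most 30 days after the 1st, so a loss needs S no later than L + 60.

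**The SAP's own example, L = 17 April 2019 (L + 30 = 17 May).**

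| True start | Recorded as | Imputed | Window end, SAP | Window end, true | Days lost |
|---|---|---|---|---|---|
| 30 April | April | 17 April | 16 April | 29 April | 13 |
| 1 May | May | 1 May | 30 April | 30 April | 0 |
| 10 May | May | 1 May | 30 April | 9 May | 9 |
| 31 May | May | 1 May | 30 April | 17 May | 17 |
| 10 June | June | 1 June | 17 May | 17 May | 0 |

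In the first row the window closes before last administration but after the last 177Lu-PSMA-617 dose of 15 April.

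**Average over dates.** I enumerated every L in 2019 against every gap S − L from 1 to 90 days. The grid and equal weighting are assumptions.

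| Gap to new therapy | Mean days lost | Window closes before L |
|---|---|---|
| 1–30 days | 10.1 | 49% |
| 31–60 days | 5.1 | 0% |
| 61–90 days | 0 | 0% |

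By branch, the mean loss is 10.5 days for same-month dates and 4.0 days for other-month dates, the latter above zero in 39% of date pairs.

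**Alternatives, gaps of 1 to 45 days (also assumed).** The mean window after L is 19.7 days with true dates, 10.0 under the SAP rule (closing before L in 33% of pairs) and 26.4 with last-day-of-month imputation. Flooring the imputed date at L + 1 alone gives 10.3. That repairs the off-by-one and little else, so the EOT visit date has to do the rest.

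**What is and is not cut.** Affected: the randomized-treatment TEAE summaries of SAP 9.2.4. Not cut by this date: death summaries (SAP 9.2.5) and laboratory summaries (SAP 9.3), which keep a fixed 30 days; long-term follow-up AE tables, which use their own CRF page; and listings, where non-TEAEs are flagged. SAP 9.2.7 counts safety topics of interest over an on-treatment period that it does not tie to this window, so I leave those aside.

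**The case against.** A reader might infer that these AEs vanish from every AE table, or that the window closes before the last radioligand dose. The documents support neither. Events still present in long-term follow-up can be tabulated there: "AE summaries for Long-term Follow up will include new and existing AEs during the long-term follow-up period captured on the Long-Term Follow up CRF page". Deaths and laboratory toxicity are summarized over an untruncated 30 days. Because last administration is the later of two dates, the window precedes the last 177Lu-PSMA-617 dose only when that dose is itself the last administration. These limits stand. The long-term follow-up route is only a partial rescue, since SAP 9.2.6 captures term and grade alone, without seriousness or relatedness, and an AE that resolved before follow-up may not appear.

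It can also be said that the EOT visit is planned at about 30 days and new therapy comes after it, so most starts should fall beyond 30 days, where the window never closes before L and the mean loss on the grid is 5.1 days or zero. This stands as a caution on the averages. It does not remove the defect, because the visit may come earlier when therapy is about to start, and losses remain possible up to 60 days.

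A difference between arms is tempting to infer but is not shown: the documents give neither the timing of new therapy nor the frequency of partial dates by arm.

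Finally, the window excludes events after new therapy on purpose. Imputing the last day of the month overshoots (26.4 against 19.7 days) and could count toxicity of the new therapy as TEAEs. That is a good reason not to make it the primary rule.

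**Conclusion.** The point holds in limited form. A same-month partial date always closes the randomized-treatment TEAE window one day before last administration. A partial date in a later month can shorten the window by up to 30 days but never past last administration. Both results follow from the text of SAP 5.2 and 9.2.1 and need no assumption about data.

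Exposure is confined to patients with a missing day whose new therapy starts within about 60 days of last administration. The average losses rest on assumed gaps of 1 to 45 or 1 to 90 days with equal weight. Without a count of partial dates, neither the number of AEs lost nor any shift between arms can be stated. The rPFS and OS analyses do not use this rule.

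**What to change.** In SAP 5.2, for TEAE assignment only:

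1. Impute a missing therapy day no earlier than the day after the later of the date of last administration and the recorded EOT visit, limited to the last day of the recorded month. State that the resulting window never closes before last administration; this must override the month limit when last administration falls on the last day of the month. With L = 17 April 2019 and a hypothetical EOT visit on 26 April, an April date would be imputed as 27 April and the window would run to 26 April instead of 16 April.
2. Add a sensitivity TEAE table with last-day-of-month imputation, still capped at 30 days after last administration.
3. Amend the sentence that restricts imputed dates so that it allows this use, and add a rule for a missing month.

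The cost is a few sentences and one extra table, using dates already collected. The downside is that a few AEs arising after the true start of new therapy may be counted as TEAEs. Reporting the number of partial dates by arm would show whether that, or the present loss, matters.

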5.3 Definition of Populations

5.3.1 Efficacy Populations

- **Full Analysis Set (FAS):** All randomized patients. Patients will be included in the treatment arm to which they were randomized regardless of actual treatment received. This is an intent to treat analysis set. This analysis set will be used for the primary analysis of OS.
- **PFS Full Analysis Set (PFS-FAS):** All patients randomized on or after 5 March 2019. Patients will be included in the treatment arm to which they were randomized regardless of actual treatment received. This analysis set will be used for the primary analyses of rPFS and all secondary endpoints excluding ORR and DCR.
- **Response Evaluable Analysis Set:** The subset of patients in the PFS-FAS with evaluable disease by RECIST at baseline (i.e. at least one target and/or non-target lesion per independent central review radiologist assessment used as the final radiology assessment. See section 8.1 for details on how the final radiology assessment is selected.). Patients will be included in the treatment arm to which they were randomized. Soft tissue response as measured by RECIST will be assessed in this dataset. This analysis set will be used for the primary analyses of ORR and DCR.

